1.0 LIST OF ABBREVIATIONS

Abbreviation	Definition
AE	Adverse Event
BUP	Buprenorphine
CCTN	Center for Clinical Trials Network
CoC	Certificate of Confidentiality
CRF	Case report form
CTN	Clinical Trials Network
DSMB	Data and Safety Monitoring Board
GCP	Good Clinical Practice
HHS	Department of Health and Human Services
HIPAA	Health Insurance Portability and Accountability Act
IRB	Institutional review board
ITT	Intent-to-Treat
LI	Lead Investigator
MOUD	Medication for opioid use disorder
NIDA	National Institute on Drug Abuse
OHRP	Office for Human Research Protections
OOTAS	Opioid Overdose & Treatment Survey
OUD	Opioid use disorder
OVN	Ohio Valley Node
PI	Principal Investigator
PP	Pregnant and postpartum
PRISM	Psychiatric Research Interview for Substance and Mental Disorders
QA	Quality Assurance
RA	Research assistant
RCT	Randomized controlled trial
SAE	Serious Adverse Event
SAMHSA	Substance Abuse and Mental Health Services Administration
SOP	Standard Operating Procedure
SUD	Substance Use Disorder
TOME	Personally-Tailored Opioid-overdose and Medication for opioid use disorder (MOUD) Education
UC	University of Cincinnati

2.0 STUDY SCHEMA

Figure 1. Study Schema

3.0 STUDY SYNOPSIS

3.1 Study Objectives

CTN-0150 includes two objectives:

- Primary Objective: To evaluate the ability of the Personally-Tailored Opioid-overdose and Medication for opioid use disorder (MOUD) Education (TOME) intervention to increase MOUD and opioid-overdose knowledge in pregnant and postpartum (PP) persons.
- Secondary Objective: To evaluate the ability of TOME to decrease MOUD-related internalized stigma and expected difficulty in avoiding drug use.

3.2 Study Design

This is an intent-to-treat, two-arm, open-label, randomized controlled trial. Eligible participants will be randomized in a 1:1 ratio to TOME or Control, balancing on site. Participants will receive the assigned intervention following randomization and will complete a three week follow-up assessment.

3.3 Study Population

Approximately 120 PP persons will be randomized into the trial. CTN is conducting the Medication treatment for Opioid-dependent expectant Mothers (MOMs; CTN-0080) trial to compare mother and infant outcomes of pregnant persons with OUD treated with extended-release buprenorphine (BUP), relative to sublingual BUP. This study will be conducted with six CTN-0080 sites with sufficient census to randomize approximately four participants per month. Eligible participants will be pregnant or within 12 months postpartum and will be enrolled in MOUD treatment.

3.4 Treatments

All randomized participants will be offered naloxone. All participants will complete an opioid-overdose and MOUD knowledge assessment during baseline. TOME participants will be offered a 15-minute intervention in which a trained research staff member reviews personal feedback reports with the recipient to provide information on the items missed on the knowledge assessment. Control participants will be offered three SAMHSA handouts: 1) “Opioid Overdose Prevention Toolkit: Safety Advice for Patients and Family Members”; 2) “Opioid Overdose Prevention Toolkit: Recovering from Opioid Overdose”; and 3) “Medication-Assisted Treatment for Opioid Addiction: Facts for Families and Friends”.

3.5 Assessments

The primary outcome is MOUD knowledge score. The key secondary outcome is opioid-overdose knowledge score. The baseline and 3-week follow-up assessments will ideally occur at the clinic site; however, these visits may occur in whole or in part via telemedicine, at other institutionally-affiliated clinical sites, or elsewhere in the community (including, but not limited to, home visits or other community sites affording appropriate safety and confidentiality) as permitted by the institution and other regulatory bodies.

3.6 Primary Analysis

Baseline-Week-3 difference in MOUD knowledge will be tested using linear regression at the 5% Type I error rate (two-sided) for the intent-to-treat population.

4.0 BACKGROUND AND RATIONALE

From 2010 to 2017, opioid-related maternal deaths increased by 220%.¹ Drug overdose deaths, particularly deaths involving synthetic opioids like fentanyl, reached record highs in 2020 and 2021;² drug overdose is now a leading cause of pregnancy-associated mortality in the United States.³ Interventions to decrease overdose risks in pregnant and postpartum (PP) persons are lacking and are needed in order to address the epidemic of opioid-related overdoses.³ Our team has developed and tested a brief personally-tailored opioid overdose prevention education and naloxone distribution (PTOEND) intervention that can be administered by bachelor's level staff.^{4,5} Our PTOEND intervention was designed to expand harm reduction by not only encouraging the use of naloxone but also educating individuals about factors that increase risk for opioid-overdose, including modifiable behaviors that increase risk. In addition, the PTOEND was designed to promote medication for opioid use disorder (MOUD) engagement, which is effective for preventing opioid-overdoses^{6,7} but is underutilized,⁸ in part due to inaccurate perceptions including misconceptions about its side effects and lack of efficacy.⁹⁻¹¹ The results of a pre-post study of PTOEND suggested that it significantly increased opioid-overdose and MOUD knowledge and increased treatment readiness in out-of-treatment adult illicit opioid users having experienced an opioid-overdose.⁵ In addition, the MOUD education intervention was found to significantly decrease expected difficulty in avoiding drug use,⁵ which is important since improved self-efficacy has been associated with improved substance use outcomes.¹²

The initial study of PTOEND was with out-of-treatment active opioid users but it is also applicable for people enrolled in MOUD. First, while MOUD significantly decreases the risk of opioid-overdose, people enrolled in MOUD still overdose and the risk of overdose is heightened when MOUD is discontinued.¹³ Opioid-overdose education, including information about risk factors for overdose, has been found to decrease overdose-risk behaviors⁵ and, thus, would be expected to reduce opioid-overdose risk in individuals who continue to use illicit opioids while enrolled in MOUD or who relapse when they stop MOUD treatment. Second, the elements of PTOEND that increased readiness for MOUD should also serve to improve engagement and retention in MOUD. While the optimal length of MOUD has not been determined, a 6-month minimum is recommended.¹⁴⁻¹⁶ Six month MOUD retention estimates vary but research suggests an estimated 6-month retention rate of 50% for methadone¹⁷ and < 50% for buprenorphine.¹⁸ There is consensus that retention needs to be improved but no evidence-based interventions for increasing MOUD retention have been established.¹⁹ Stigma is one of the most commonly cited barriers to MOUD retention by individuals with OUD.²⁰⁻²² The PTOEND, which corrects stigma-eliciting misperceptions (e.g., MOUD is "just replacing one drug with another", etc.), is hypothesized to reduce internalized stigma. Another common barrier to MOUD engagement/retention is inaccurate perceptions of MOUD – including myths about its side effects and lack of efficacy.²¹ We evaluated the impact of the MOUD education component in a small (N=20) pre-post study of recently-enrolled MOUD patients and found a significant increase in MOUD knowledge after MOUD education ($p < .01$). PTOEND has been found to increase patient's belief in their ability to avoid drug use, which may be the result of correcting MOUD myths, including providing information about its effectiveness.⁵

The present trial will test a modified version of the PTOEND intervention, referred to as the personally-Tailored Opioid-overdose and MOUD Education (TOME) intervention, in pregnant and postpartum (PP) persons. Modifications include updating the knowledge assessment/education to reflect changes in the drug supply (i.e., the current high prevalence of fentanyl and increasing prevalence of xylazine) and the addition of items specific to pregnancy.

5.0 STUDY OBJECTIVES

5.1 Primary Objective

The primary objective of this study is to evaluate the ability of TOME to increase MOUD and opioid-overdose knowledge in PP persons.

5.2 Secondary Objective

The secondary objective is to evaluate the ability of TOME to decrease MOUD-related internalized stigma and expected difficulty in avoiding drug use.

6.0 STUDY DESIGN

6.1 Overview of Study Design

This is an intent-to-treat, two-arm, open-label, randomized controlled trial. Eligible participants will be randomized in a 1:1 ratio to TOME or Control, balancing on site. Participants will receive the assigned intervention following randomization and will complete follow-up assessments at~ 3 weeks post-randomization. Key outcome measures are: 1) MOUD knowledge (primary); and 2) opioid-overdose knowledge (key secondary).

6.2 Number of Sites and Participants

Approximately 120 participants, recruited from approximately 6 sites, will be randomized into the trial. Patients enrolled in MOUD (either buprenorphine or methadone) at the study site who are either pregnant or within 12 months postpartum will be recruited for the study. Participants may be recruited from a variety of other sources, including advertising if needed. Recruitment advertisements will be approved by the Institutional Review Board (IRB). Efforts will be made to recruit a study sample that reflects, or exceeds, the proportion of minorities in treatment at the sites.

6.3 Study Duration

Enrollment is expected to take place over a period of approximately 6 months. Duration of study participation will be approximately 3 – 4 weeks.

6.4 Site and Participant Selection

6.4.1 Site Selection

CTN is conducting the Medication treatment for Opioid-dependent expectant Mothers (MOMs; CTN-0080²³) trial to compare mother and infant outcomes of pregnant persons with OUD treated with extended-release buprenorphine (BUP), relative to sublingual BUP. CTN-0080 has completed recruitment but has a very long active treatment phase (i.e., through 12 months postpartum). Staff need to be retained through the CTN-0080 active treatment phase. The proposed study would be conducted with six CTN-0080 sites with sufficient census to enroll randomize approximately four participants per month.

6.4.1.1 *Site Characteristics*

Participating sites should:

1. have been a site in CTN-0080;
2. have sufficient census to meet the target randomization of 4 per month

6.4.2 Participant Selection

6.4.2.1 *Inclusion Criteria*

Potential participants must be:

1. 18 years of age or older;
2. pregnant or be within 12 months postpartum;

3. enrolled in MOUD (either buprenorphine or methadone) at the study site or affiliated clinic where enrollment can be confirmed;
4. able to understand the study, and having understood, provide written informed consent in English

6.4.2.2 *Exclusion Criteria*

[figure not shown]
Potential participants must not:

1. have suicidal or homicidal ideation requiring immediate attention
2. be currently in jail, prison, or any inpatient overnight facility as required by court of law or have pending legal action

6.5 Potential Follow-up Trial

The conceptual model for TOME's hypothesized ability to increase MOUD treatment retention is provided in Figure 2. The present pilot trial is being conducted with active CTN-0080 study sites and is limited to the time remaining for CTN-0080 implementation. As a consequence, the pilot trial is limited to a 3-week follow-up and, thus, is not testing TOME's ability to increase MOUD retention. Instead, this pilot trial is testing TOME's impact on the two hypothesized mediators by which TOME would improve retention. Finding that TOME significantly increases MOUD knowledge and significantly decreases MOUD stigma would provide support for a follow-up trial to test TOME's ability to improve MOUD retention rates.

Fig. 2: Conceptual Model of TOME's Retention Impact

7.0 STUDY MEASURES

7.1 Key Outcome Measures of the Primary Objective

7.1.1 Primary Outcome - MOUD knowledge score

The primary outcome is MOUD knowledge as measured by the Opioid Overdose and Treatment Awareness Survey (OOTAS) knowledge evaluation. The OOTAS is comprised of 4 sections: 1) opioid-overdose risk factors; 2) signs of an opioid-overdose; 3) how to respond to an opioid-overdose; and 4) misconceptions about MOUD.⁴ The OOTAS has been successfully used to measure MOUD knowledge and knowledge change in two published studies^{4,5} and in a small (N=20) pre-post study of recently-enrolled MOUD patients, which found a significant increase in MOUD knowledge after MOUD education ($p<.01$). For the present trial, the OOTAS has been modified to include two additional questions specific to pregnancy (i.e., are methadone and BUP recommended during pregnancy and can babies be born addicted as a result of taking methadone or BUP during pregnancy). The modified OOTAS includes 10 true-false questions to assess MOUD knowledge, yielding a potential score of 0-10.

7.1.2 Key Secondary Outcome – Opioid-overdose knowledge score

The key secondary outcome is opioid-overdose knowledge as measured by the first three sections of the OOTAS. The OOTAS has been successfully used to measure opioid-overdose knowledge and knowledge change in two prior studies conducted with individuals with OUD. For the present trial, the OOTAS has been modified to include two additional questions to assess the participant's knowledge of the increase risk of opioid-overdose with fentanyl and potential increased risk with xylazine. The modified OOTAS includes 31 true-false questions to assess opioid-overdose knowledge, yielding a potential score of 0-31.

7.2 Secondary Outcome Measures

7.2.1 MOUD Internalized Stigma

The Methadone Maintenance Treatment Stigma Mechanisms Scale (MMT-SMS) is a self-report questionnaire assessing three dimensions of stigma: anticipated, enacted, and internalized stigma.²⁴ The MMT-SMS has demonstrated good internal consistency and validity.²⁴ The MOUD education is expected to decrease internalized stigma by countering stigma-inducing myths (e.g., methadone/BUP is just replacing one drug with another, etc.) and, thus, the internalized stigma score is the outcome of interest. The MMT-SMS was designed for use with any MOUD medication and the wording will be modified to assess stigma related to the medication that the participant is receiving.

7.2.2 Drug Self-efficacy

Self-efficacy in avoiding drug use will be assessed with the Thoughts about abstinence (TAA) instrument.²⁵ This measure assesses the participant's desire to quit, expected success in quitting and estimated difficulty in avoiding drug use.²⁵ Our MOUD education intervention has been found to increase expected success in avoiding drug use as measured by the TAA.⁵

7.3 Safety Measures of the Primary Objective

7.3.1 Adverse Events (AEs)

There are not specific guidelines for adverse event (AE) and serious adverse event (SAE) reporting for behavioral trials but it is important to assess for potential AEs that could result from exposure to a behavioral intervention.²⁶ TOME is a low-risk intervention but staff will assess for two AEs that would be of clinical import: 1. Suicidal ideation and 2. Homicidal ideation. Research suggests that using the FDA definition of SAEs (i.e., an adverse event that results in any of the following outcomes: death; life threatening; requires hospitalization, initial or prolonged; results in disability; congenital anomaly; requires intervention to prevent permanent impairment or damage; or other significant medical event) for behavioral trials with substance using populations does not produce meaningful safety information in that many SAEs are reported but none judged to be related to the intervention.²⁷ SAEs will only be reported for events related to a study-defined AE (e.g., hospitalization due to suicidal ideation, etc.).

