11.16.2 Adverse Events (AEs)

There are not specific guidelines for adverse event (AE) and serious adverse event (SAE) reporting for behavioral trials but it is important to assess for potential AEs that could result from exposure to a behavioral intervention.²⁶ TOME is a low-risk intervention but staff will assess for two AEs that would be of clinical import: 1. Suicidal ideation and 2. Homicidal ideation. Research suggests that using the FDA definition of SAEs (i.e., an adverse event that results in any of the following outcomes: death; life threatening; requires hospitalization, initial or prolonged; results in disability; congenital anomaly; requires intervention to prevent permanent impairment or damage; or other significant medical event) for behavioral trials with substance using populations does not produce meaningful safety information in that many SAEs are reported but none judged to be related to the intervention.²⁷ SAEs will only be reported for events related to an AE (e.g., hospitalization due to suicidal ideation, etc.). The study staff will be trained to monitor for and report AEs and SAEs. Additionally, as applicable, sites will submit reporting of AEs/SAEs according to IRB requirements. Each of the sites has established practices for managing medical and psychiatric emergencies, and the study staff will continue to utilize these procedures. Treatment providers at each site will be responsible for monitoring participants for possible clinical deterioration or other problems, and for implementing appropriate courses of action.

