16.5 Regulatory Issues

1. Reporting of adverse events (AEs) and serious adverse events (SAEs) to the IRB, NIDA, and the FDA: All study-defined SAEs will be reported to the participating site's IRB and NIDA within 72 hours of their discovery. This is a behavioral study and so FDA reporting is not required. All participant information will be de-identified when reporting SAEs. In a case where a reported SAE may be very severe and/or require a protocol amendment to be made, [name] may request an ad hoc review by the DSMB. All study-defined AEs and SAEs will be entered into a database that is de-identified and password protected to ensure confidentiality.
2. Reporting of IRB action to NIDA: All communications with and actions of the IRB will be kept in a regulatory binder specific for this study. Any protocol changes, amendments, or deviations will be submitted to the IRBs and NIDA and the IRB's actions will then be reported to NIDA. Any other IRB actions will be submitted to NIDA.
3. Report of changes or amendments to the protocol: All changes and amendments to the protocol will be submitted to the IRBs and NIDA. Only after IRB and NIDA approvals are granted will the changes and amendments be implemented.
4. Trial stopping rules: Individual study participants will be informed of their right to discontinue study participation at any time during the study. The PI may discontinue a participant from the trial if deemed clinically appropriate. NIDA has the right to discontinue the investigation at any time.
5. Disclosure of conflict of interest: The investigators have no conflicts of interest.

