2. **Collection and management of AEs and SAEs:** In general, the risks associated with trials employing behavioral interventions are presumed minimal relative to those evaluating pharmacologic interventions. An adverse event (AE) for this trial testing a low risk, education intervention is defined as: 1. Suicidal ideation and 2. Homicidal ideation.

SAEs will only be reported for events related to an AE (e.g., hospitalization due to suicidal ideation, etc.). We will use FDA criteria for SAEs (i.e., an adverse event that results in any of the following outcomes: death, life threatening event, initial or prolonged hospitalization, disability, congenital anomaly, intervention to prevent permanent impairment or damage, or other significant medical event). The study staff will be trained to monitor for and report AEs and SAEs. Additionally, as applicable, sites will submit reporting of AEs/SAEs according to IRB requirements. Each of the sites has established practices for managing medical and psychiatric emergencies, and the study staff will continue to utilize these procedures. Treatment providers at each site will be responsible for monitoring participants for possible clinical deterioration or other problems, and for implementing appropriate courses of action.

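### An opioid overdose without established suicidal or homicidal ideation falls outside the study's AE/SAE system, although the protocol treats overdose as a foreseeable harm that the intervention aims to reduce

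*Combined protocol and SAP*

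**What the plan says.** Section 7.3.1 limits adverse events to two: "staff will assess for two AEs that would be of clinical import: 1. Suicidal ideation and 2. Homicidal ideation". The Data and Safety Monitoring Plan makes this the definition (16.6, item 2): "An adverse event (AE) for this trial testing a low risk, education intervention is defined as: 1. Suicidal ideation and 2. Homicidal ideation".

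Serious events are tied to that list. Section 7.3.1 states that "SAEs will only be reported for events related to a study-defined AE (e.g., hospitalization due to suicidal ideation, etc", and 11.16.2 likewise that "SAEs will only be reported for events related to an AE (e.g., hospitalization due to suicidal ideation, etc". Section 16.6 adds "We will use FDA criteria for SAEs", which bring in death, life-threatening events and hospitalization, but only for events already related to a study-defined AE.

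Section 16.5, item 1 applies the 72-hour report to the IRB and NIDA to study-defined SAEs. On the safety database it says "All study-defined AEs and SAEs will be entered into a database that is de-identified and password protected". The chi-square comparison in 10.3 and 16.3 is of AEs, so of the two ideation events.

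Sections 7.3.1 and 11.16.2 give a reason for the narrow rule: in behavioral trials with substance-using populations, full FDA-type SAE reporting has produced many reports, none of them attributed to the intervention.

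On overdose, section 4.0 says that "drug overdose is now a leading cause of pregnancy-associated mortality in the United States" and that "people enrolled in MOUD still overdose and the risk of overdose is heightened when MOUD is discontinued".

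**The concern.** The background presents overdose as a foreseeable and serious event in this population, including among people in treatment. The education is meant to reduce it, opioid-overdose knowledge is the key secondary outcome (7.1.2), and every randomized participant is offered naloxone (9.0). Yet the safety definitions do not mention it.

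A site that follows the plan exactly would have no study-defined event to record for a participant hospitalized after an unintentional overdose. An overdose of undetermined intent would count only if ideation were established, which may not be possible after a death. The final safety account could then state that there were no AEs or SAEs although overdoses had occurred during follow-up.

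**Working it through.** The plan gives no figure for overdose, so there is none to reproduce. The check is a reading of the safety provisions, followed by a calculation of scale.

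**Step 1. Follow an overdose without established ideation through the AE/SAE system.**

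- AE definition (7.3.1, 11.16.2, 16.6 item 2): not one of the two events, so not an AE.
- SAE rule (same sections): not related to a study-defined AE, so not reportable as an SAE even if it led to hospitalization or death.
- 72-hour report and safety database (16.5 item 1): both are written for study-defined events, so they do not apply.
- AE comparison (10.3, 16.3 item 4): not counted.

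**Step 2. Look for another measure that asks about it.** Table 1 (8.4) schedules four measures at Week 3: adverse events, the OOTAS (a knowledge test), the MMT-SMS (stigma) and Thoughts about abstinence. Substance use history is collected at baseline only and asks about frequency of use (7.4.2). No described Week 3 item asks about overdose.

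**Step 3. Look for indirect or discretionary routes.**

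- The Study Completion form records why a participant ended early (7.5), and disposition goes into the final report (16.8 item 3). A death could appear there, but no cause-of-death field is described.
- Unanticipated problems and local SAE reports go to the IRB under its own procedures (11.1), and sites report AEs and SAEs as the IRB requires (11.16.2).
- Site investigators report to the sponsor changes that raise participant risk (11.12).
- Treatment providers monitor for clinical problems (11.16.2).
- An ad hoc meeting of the MOMs DSMB can be requested (11.16.1, 16.9). An AE or SAE is given there only as an example of a trigger.

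None of these names overdose or asks about it. The only item that 16.8 names for scheduled review is breaches of confidentiality.

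**Step 4. Scale.** Inputs: about 120 participants (6.2) and 3 to 4 weeks of participation (6.3). The overdose rate is an assumption, shown as a range because the documents give none.

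Person-years = participants × weeks / 52:
- 120 × 3 / 52 = 6.92
- 120 × 4 / 52 = 9.23

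Expected events = person-years × rate. Chance of at least one = 1 − exp(−expected), assuming a Poisson count.

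| Assumed rate per 100 person-years | Expected, 3 weeks | Chance of ≥1, 3 weeks | Expected, 4 weeks | Chance of ≥1, 4 weeks |
|---|---|---|---|---|
| 1 | 0.07 | 7% | 0.09 | 9% |
| 5 | 0.35 | 29% | 0.46 | 37% |
| 10 | 0.69 | 50% | 0.92 | 60% |
| 20 | 1.38 | 75% | 1.85 | 84% |

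At the middle and upper assumed rates at least one overdose is quite plausible. At no rate in the range is there enough information to compare arms.

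**The case against.** The strongest reply is that this is a deliberate choice, stated consistently in three places and with a reason. The aim is to capture harms that exposure to a behavioral intervention could cause, and the documents offer no mechanism by which a 15-minute educational review would cause an overdose. Any extra reports would probably be judged unrelated, which is the protocol's own argument. This stands to the extent that the omission contradicts nothing in the plan and is not a drafting error. But the argument supports a short list. It does not explain leaving off the one event that the education targets, and the documents never discuss overdose as a safety event.

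A second reply is that a reader might infer that an overdose would go wholly unrecorded and unreported. The documents do not support that: the routes in step 3 exist, and a fatal overdose in particular could surface through early termination or disposition. What they lack is any systematic question or named category.

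A third is that a reader might infer that the case for a follow-up trial rests on a safety statement that this gap would undermine. Section 6.5 rests that case on increased MOUD knowledge and decreased stigma, so the inference fails.

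Finally, a Week 3 question reaches only those who attend. With at least 88% attendance assumed (10.4), up to about 14 of 120 (120 × 0.12 = 14.4) would not be asked, and a death cannot be self-reported. This is a fair limit on the question alone, and it is why the definition must change as well.

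**Conclusion.** The point holds as a gap in safety capture. Under the plan as written, an overdose without established ideation is not a study-defined AE or SAE, is not asked about at Week 3, is not in the AE comparison and is not subject to the 72-hour report. It can come to light only indirectly or at discretion.

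The size is modest: about 0.07 to 1.85 expected overdoses. That range assumes all 120 participants are followed for 3 to 4 weeks and a constant rate of 1 to 20 per 100 person-years, which is not taken from the documents. Overdose is not an efficacy endpoint (the primary outcome is MOUD knowledge), so a reader should not infer bias in the primary analysis or a lost comparison of arms. What is affected is the completeness of the safety description. The change is a cheap improvement rather than the correction of an error.

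**What to change.** 1. In 7.3.1, 11.16.2 and 16.6 item 2, add a third study-defined AE: opioid overdose, fatal or non-fatal, whatever the intent. The existing SAE sentence and the 72-hour rule in 16.5 then apply without further change. State that it counts whether the site learns of it at a visit or in some other way.
2. Add one overdose item to the Week 3 AE form.
3. In 10.3 and 16.3, state that overdoses are reported as a descriptive listing by arm, separate from the chi-square test.

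The rest of the narrow definition can stay as it is. The cost is protocol wording in a few places, one REDCap item and perhaps one or two extra reports, most of which would probably be judged unrelated to the intervention.
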